### **10.3.2 Evaluable for Objective Response**

Only those patients who have measurable disease present at baseline, have received at least one cycle of treatment (magrolimab+obinutuzumab) therapy, and have had their disease re-evaluated will be considered evaluable for response. (NOTE: Patients who exhibit objective disease progression after receiving at least one cycle of magrolimab+obinutuzumab will also be considered evaluable.)

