### 6.3.6.8 Objective Tumor Response Rate

The proportion of patients who achieve at least a partial response (PR) to therapy.

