## **10.3 POPULATIONS FOR ANALYSES**

### **10.3.1 Evaluable for Toxicity**

All patients who have received at least one dose of any of the study drugs will be evaluable for toxicity.

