### **10.3.3 Evaluable Non-Target Disease Response**

Patients who have lesions present at baseline that are evaluable but do not meet the definitions of measurable disease, have received at least one cycle of therapy, and have had their disease re-

evaluated will be considered evaluable for non-target disease response assessment. The response assessment is based on the presence, absence, or unequivocal progression of the lesions.

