### **10.4.3 Analysis of the Secondary Endpoints**

The type, number and frequency of DLTs to doublet combination therapy (during the ‘window’) will be reported and described. The ORR, and CR rate will be determined and reported from individual cohorts and histological diagnosis. CMR rate by flow cytometry or similar assays as they become available will be determined and reported separately for the CLL cohort. Responses will also be reported along with 95% confidence intervals, with waterfall plots, when appropriate. The duration of response (DOR; beginning at the date clinical response is first identified), progression free survival (PFS), event-free survival (EFS), and overall survival (OS) will be estimated using Kaplan-Meier curves, along with 95% confidence intervals at the median when appropriate.

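### The only response population (10.3.2) would drop treated early exits and unassessed patients from ORR and CR rate, and it fits neither eligibility nor the triplet endpoint

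*Combined protocol and SAP*

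**What the plan says.** Section 10.3 of the combined protocol and SAP defines three populations.

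- **Toxicity (10.3.1):** "All patients who have received at least one dose of any of the study drugs will be evaluable for toxicity".
- **Objective response (10.3.2):** it opens "Only those patients who have measurable disease present at baseline" and adds that they must "have received at least one cycle of treatment (magrolimab+obinutuzumab) therapy, and have had their disease re-evaluated will be considered evaluable for response". A note keeps one group of early failures: "Patients who exhibit objective disease progression after receiving at least one cycle of magrolimab+obinutuzumab will also be considered evaluable".
- **Non-target disease response (10.3.3):** for lesions that are evaluable but not measurable. These patients must also "have received at least one cycle of therapy" and be re-evaluated, and "The response assessment is based on the presence, absence, or unequivocal progression of the lesions".

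Section 10.4.3 states: "The ORR, and CR rate will be determined and reported from individual cohorts and histological diagnosis". It adds 95% confidence intervals but cites none of the three populations. Section 6.3.6.8 defines the objective response rate as "The proportion of patients who achieve at least a partial response (PR) to therapy", and 6.3.6.6 likewise refers the CR rate simply to patients.

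Four other places bear on the point. Section 10.1.2 makes ORR after the triplet the secondary endpoint. Section 10.4.9 lists ORR after the doublet as exploratory. Section 6.3.6.1 counts best response from the start of treatment. Section 2.1.1.4 admits patients with evaluable disease and makes measurable disease optional.

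**The concern.** An analyst looking for the ORR and CR denominator will find only 10.3.2 labelled for objective response. Applying it has three consequences.

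1. Treated patients who leave, die or progress before receiving one cycle, and those never re-evaluated, are removed instead of being counted as non-responders. No section counts them as failures, although the toxicity set keeps them.
2. Patients admitted with evaluable-only disease are excluded even where section 6.3 can score them.
3. The exposure condition names magrolimab plus obinutuzumab. Expansion patients receive two doublet cycles before venetoclax, so the set can include patients who never received venetoclax. Because best response runs from the start of treatment, a response in the window can also count towards an endpoint defined after the triplet.

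At stake are the reported ORR, CR rate and their intervals. The expansion cohorts have 6 to 18 patients, so a single patient moves the figure visibly, and the interval does not reveal that anyone was left out.

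**Working it through.** **Step 1: the plan's own numbers (10.2).** Dose-finding 12 + 12 = 24. Expansion 18 + 6 + 12 + 6 = 42. Total 24 + 42 = 66, as stated. The accrual ceiling of 76 leaves 76 − 66 = 10 places for inevaluable patients and screen failures together, with no split. The plan therefore gives no expected number of patients not evaluable for response.

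**Step 2: who is in and who is out under 10.3.2.**

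| Treated patient | In the 10.3.2 set? |
|---|---|
| Progresses after at least one doublet cycle | Yes (note) |
| Stops after one cycle, with a discontinuation scan, measurable disease | Yes |
| Leaves, dies or progresses before receiving one cycle | No |
| Never re-evaluated, without documented progression | No |
| Evaluable disease only | No, if it is not measurable |
| Two doublet cycles, re-evaluated, no venetoclax, measurable disease | Yes |

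Under Appendix G, footnote 11, the first scheduled on-treatment CT comes after the two window cycles in expansion, and after Cycle 3 in dose-finding, which has no window. Section 10.3.3 does not recover the missing patients: it has the same cycle and re-evaluation conditions, and its categories contain no PR. Replacement in 3.1.1 concerns DLT evaluability only.

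**Step 3: effect of one dropped patient.** With r responders among n treated:

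- dropping one non-responder changes the rate by r/(n−1) − r/n = r/[n(n−1)];
- dropping one patient with a recorded response changes it by (r−1)/(n−1) − r/n = −(n−r)/[n(n−1)].

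The true rate of two-thirds is an assumption. Intervals are exact (Clopper-Pearson) 95%.

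| Cohort | All treated | One non-responder dropped | Shift | Shift if a responder is dropped |
|---|---|---|---|---|
| FL pooled, 18 + 6 | 16/24 = 67% (45–84) | 16/23 = 70% (47–87) | +2.9 | −1.4 |
| FL expansion | 12/18 = 67% (41–87) | 12/17 = 71% (44–90) | +3.9 | −2.0 |
| MCL expansion | 8/12 = 67% (35–90) | 8/11 = 73% (39–94) | +6.1 | −3.0 |
| MZL or CLL expansion, unpooled | 4/6 = 67% (22–96) | 4/5 = 80% (28–99) | +13.3 | −6.7 |

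Section 10.2 allows Cohort 2 to be pooled with Cohorts 4 to 6. The six Cohort 2 patients at the expansion dose may come from any of three histologies. Pooled MZL or CLL would then have between 6 and 6 + 6 = 12 patients, and the shift would lie between +13.3 and +6.1 points.

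**Step 4: chance that at least one such exit occurs.** This is 1 − (1−p)^n, with p assumed because the documents give no value. For p = 1%, 2% and 5% it is 6%, 11% and 27% with 6 patients; 17%, 31% and 60% with 18; and 21%, 38% and 71% with 24.

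**Step 5: measurable disease.** The clearest conflict is lymphoma scored by PET uptake without measurable masses. Section 2.1.1.4 admits such a patient and the PET-CT column in 6.3.1 can score the response, but 10.3.2 excludes the patient. For CLL, MCL assessed by iwCLL, and splenic MZL, the plan does not define what measurable means, so whether those patients are excluded depends on interpretation. The direction of any resulting bias is unknown.

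**The case against.** The strongest reply is that 10.4.3 never invokes 10.3.2, so the documented gap is an unnamed denominator and not a biased choice. That is correct as far as it goes, and 10.4.3 does not cite 10.3.3 either. But 10.3.2 is the only set defined for objective response, and leaving the denominator open needs the same edit.

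The second reply is that few patients are affected. Scans are scheduled at discontinuation, 3.10.1 continues follow-up for progression after treatment stops, the note in 10.3.2 keeps progressors after one cycle, and 3.1.2 lets window progressors who tolerate therapy move to the triplet. The plan also does not say whether receiving a cycle means completing it. All of this stands and limits the size.

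Third, response is secondary and explicitly preliminary. No test, threshold, power or sample size depends on it, and PFS, EFS and OS run from enrollment without this filter. An evaluable-patient analysis is also common in phase 1. This limits the consequence, but it does not explain why treated, unassessed patients should vanish from a rate.

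Two stronger readings are tempting and not supported:

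- **Always upward.** A reader might infer that the exclusion always inflates the rates. It does so only when the dropped patients have no recorded response and there is at least one responder. An early exit with a recorded response would lower the rate.
- **Size taken from discontinuation rates.** A reader might take the 7% AE discontinuation in section 1.2.4.4 (8/115) as a ceiling on exits. It comes from magrolimab plus rituximab, and section 1.2.7.1 cites 16% (34/212) for venetoclax plus obinutuzumab. Nor can these rates, or the 25% stopping threshold in 10.2, serve as the share never evaluated. They cover discontinuation at any time, and a patient who stops after one cycle and is scanned can stay in the set.

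**Conclusion.** The point holds as a conditional one. If 10.3.2 is the denominator, which is an inference, treated early exits and never-assessed patients are omitted instead of counted as failures. ORR and CR rate are then overstated when those patients have no recorded response. At an assumed two-thirds rate, one such patient adds 2.9 to 6.1 points in cohorts of 24 to 12, and 13.3 points in an unpooled cohort of 6. The number affected is unknown and probably small, and in each example the intervals before and after overlap almost entirely.

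Two mismatches are independent of how many patients leave early. The measurable-disease condition conflicts with eligibility, most clearly for PET-scored lymphoma. The doublet exposure condition, together with best response counted from the start of treatment, does not match ORR after the triplet.

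The consequence is confined to descriptive estimates and their intervals. A reader might infer that sample size or error rates are undermined. They are not, because the expansion numbers rest on expected accrual. The change is worth making before analysis because it is cheap and prevents a choice of denominator after the results are known.

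**What to change.** Amend 10.3 and 10.4.3 as follows.

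1. **Main analysis.** Report ORR and CR rate after the triplet, by cohort and histology, in all patients who received at least one dose of venetoclax. Count responses documented at assessments after the first venetoclax dose, judged against the pre-treatment baseline. Count patients with no such assessment as non-responders. Add a matching line to 6.3.6.1, which at present starts the period at the beginning of treatment.
2. **Beside it.** Report the same rates in all treated patients (the 10.3.1 definition) with the same non-responder rule.
3. **Window responses.** Report them under the exploratory doublet ORR in 10.4.9.
4. **Disease condition.** Do not require measurable disease where the applicable criteria in 6.3 can score the patient.
5. **Sensitivity analysis.** Keep the 10.3.2 set, labelled as such, and list the number of unassessed patients with the reason for each.

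This needs wording only, with no new visits, data or patients. The cost is slightly lower reported rates and one extra table.

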### **10.3.3 Evaluable Non-Target Disease Response**

Patients who have lesions present at baseline that are evaluable but do not meet the definitions of measurable disease, have received at least one cycle of therapy, and have had their disease re-

evaluated will be considered evaluable for non-target disease response assessment. The response assessment is based on the presence, absence, or unequivocal progression of the lesions.

## **10.4 STATISTICAL ANALYSES**

### **10.4.1 General Approach**

Toxicity profile of the combination therapy will be reported, and important toxicities described. Response rates will be reported as percentage, and time-to-event outcomes will be reported using Kaplan-Meier curves.

### **10.4.2 Analysis of the Primary Endpoints**

The type, number and frequency of DLTs to triplet combination therapy will be reported and described.

### **10.4.3 Analysis of the Secondary Endpoints**

The type, number and frequency of DLTs to doublet combination therapy (during the ‘window’) will be reported and described. The ORR, and CR rate will be determined and reported from individual cohorts and histological diagnosis. CMR rate by flow cytometry or similar assays as they become available will be determined and reported separately for the CLL cohort. Responses will also be reported along with 95% confidence intervals, with waterfall plots, when appropriate. The duration of response (DOR; beginning at the date clinical response is first identified), progression free survival (PFS), event-free survival (EFS), and overall survival (OS) will be estimated using Kaplan-Meier curves, along with 95% confidence intervals at the median when appropriate.

### **10.4.4 Safety Analyses**

The type, grade and frequency of toxicities will be reported. DLTs, MTD of venetoclax in combination with magrolimab and obinutuzumab; and SAEs will be reported as well.

### **10.4.5 Baseline Descriptive Statistics**

Baseline characteristic of all cohorts will be explained including demographics, prior therapies and functional status.

### **10.4.6 Planned Interim Analyses**

No interim analyses are planned

### **10.4.7 Sub-Group Analyses**

None planned.

### **10.4.8 Tabulation of Individual Participant Data**

None planned.

### **10.4.9 Exploratory Analyses**

The following are the exploratory analyses planned:

- Overall response rate (ORR) after doublet-combination therapy with magrolimab and obinutuzumab

- Complete molecular remission rate (CMR) by ctDNA assay or similar assays as they become available after doublet-combination therapy with magrolimab and obinutuzumab
- Complete molecular remission rate (CMR) by ctDNA assay or similar assays as they become available after triplet-combination therapy with magrolimab, obinutuzumab and venetoclax
- Lead time for ctDNA assay in detecting molecular relapse prior to clinical progression
- Identify potential biomarkers and molecular correlates that are associated with response and/or resistance to the study treatment
- Test immunogenicity of magrolimab and asses the effect of anti-drug antibodies (ADA) on the pharmacokinetics, pharmacodynamic markers, efficacy, and safety of magrolimab.

The ORR and CMR rates will be determined and reported from individual cohorts and histological diagnosis. Responses will also be reported with waterfall plots, when appropriate. The exploratory objectives such as seeking to identify potential biomarkers and molecular correlates that are associated with response and/or resistance to the study treatment, will be assessed using descriptive statistics as well as non-parametric methods such as exact Wilcoxon rank sum tests. The analyses will be done without formal adjustment for multiple comparisons, but in the context of the number of tests performed.

Magrolimab PK data will be summarized using summary statistics (mean, median, range, standard deviation, etc.) at each time point. The overall rate of ADA occurrence and type of ADA (e.g., transient vs persistent) will be summarized for all patients. PK in ADA positive and negative patients will be tabulated at each timepoint. If relevant, the impact of ADA occurrence on efficacy and safety will be assessed through summary statistics.

## **11 COLLABORATIVE AGREEMENTS**

### **11.1 CLINICAL TRIAL AGREEMENT (CTA)**

#### **11.1.1 Gilead Sciences, Inc.**

There is a CTA with Gilead Sciences, Inc. (#01181-20).

#### **11.1.2 Genentech**

There is a CTA with Genentech, Inc. (#01182-20).

## **12 HUMAN SUBJECTS PROTECTIONS**

### **12.1 RATIONALE FOR PATIENT SELECTION**

This trial is designed as a novel-novel targeted therapy with magrolimab as backbone for patients with indolent lymphomas. Median age for all 4 histologies included in this study are over 60 years of age and male predominance is noted in MZL and CLL. Pregnant or nursing mothers are excluded because of the potential teratogenic effects of therapy. Given the small number of patients on our study, we expect a gender-even to a slightly male predominant patient population for our study.

## **12.2 PARTICIPATION OF CHILDREN**

Since safety data is not available for magrolimab in children, patients <18 years of age will be excluded from the study. Also, most of the histologies of indolent lymphomas we are testing are rare in children.

## **12.3 RISK/BENEFIT ASSESSMENT**

### **12.3.1 Known Potential Risks**

The most common (>10%) adverse reactions with magrolimab are anemia (43%), nausea (41%), fatigue (30%), constipation (39%), diarrhea (39%), infusion-related reactions (33%), headache (32%), dyspnea (30%), pyrexia (39%), cough (27%), thrombocytopenia (25%), decreased appetite (25%), febrile neutropenia (25%), chills (23%), vomiting (23%), dizziness (20%), and hypokalemia (21%), and bilirubin increase (15%), and pneumonia (10%). Other common AEs with magrolimab include hemolysis ( $\geq 1\%$  and <10%, SAR 1.2% serious), sepsis ( $\geq 1\%$  and <10%, 0.4% serious), and hypotension ( $\geq 10\%$ , 0.2% serious). Common AEs with venetoclax-obinutuzumab combination were neutropenia, thrombocytopenia, diarrhea, infections, fatigue and nausea. Severe neutropenia may occur with magrolimab use. Grade 3 (absolute neutrophil count [ANC] 500 to <1000 cells/uL) and Grade 4 (ANC <500 cells/uL) have been reported. Additionally, fatal events of febrile neutropenia have been reported in patients treated with magrolimab. Close hematological monitoring will be performed for all patients during treatment (at least once a month while on therapy). In cases of neutropenia, consider antimicrobial prophylaxis and administration of granulocyte colony-stimulating factor (G-CSF) if clinically appropriate. If febrile neutropenia occurs, administer antibiotics and antimycotics. Dose modifications/delays will be per Section [3.3.2](#).

Serious infections (Grades 3 or 4) have been reported in patients treated with magrolimab, including fatal events of pneumonia and sepsis. Patients will be regularly monitored for signs and symptoms of infection during monthly clinic visits while on therapy. For patients with prolonged neutropenia or patients at risk, infection prophylaxis using appropriate antibiotics will be considered in accordance with current guidelines. Dose modifications/delays will be per Section [3.3.2](#).

TLS has been observed with venetoclax, but rigorous precautions, slow ramp-up of dose and early detection and treatment has improved the safety profile. Individually, both magrolimab (in FL) and venetoclax (in CLL, FL, MZL and MCL) have shown promising activity.

As noted in Section [3.2](#), premedication will be given to reduce the risk of AEs occurring. Subjects will be monitored closely, and manufacturer recommendations for delaying and discontinuing study medications and initiating supportive therapy will be followed.

#### **12.3.1.1 Biopsy Risk**

The risks associated with biopsies are pain and bleeding at the biopsy site. In order to minimize pain, conscious sedation or local anesthesia will be used. Rarely, there is a risk of infection at the sampling site. CT guidance may be used for biopsies.

#### **12.3.1.2 Conscious Sedation**

The common side effects of conscious sedation include drowsiness, delayed reflexes, hypotension, headache, and nausea. These are generally mild and last no more than a few hours.

#### 12.3.1.3 Bone Marrow Biopsy

Bone marrow biopsy is minimally invasive and is typically a very safe procedure. Usually, the hipbone is numbed with anesthesia. Using a needle, the solid and liquid portion of bone marrow is taken out. This procedure causes some pain. Very rarely, infection or bleeding may occur at the needle site.

#### 12.3.1.4 Radiation Risk

The study will involve radiation from the following sources:

- Up to 7 CT scan of chest abdomen pelvis (1 during screening)
- Up to 4 [F]-FDG-PET/CT
- Up to 2 CT-guided biopsies as referenced above

Subjects in this study may be exposed to approximately 14.1 rem. This amount is more than would be expected from everyday background radiation. Being exposed to excess radiation can increase the risk of cancer. The risk of getting cancer from the radiation exposure in this study is 1.4 out of 100 (1.4%) and of getting a fatal cancer is 0.7 out of 100 (0.7%).

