## 3 STUDY IMPLEMENTATION

### 3.1 STUDY DESIGN

This is a non-randomized, open-label, four arm, single institution phase 1 study of magrolimab, obinutuzumab, and venetoclax for patients with relapsed/refractory indolent B-cell malignancies. The study involves a novel design that includes a treatment window with a doublet in order to maximize the potential for translational research as well as a safety period to assess the safety of the triplet combination of venetoclax added to magrolimab with obinutuzumab in different disease sub-types.

Research biopsies of lymph nodes and/or bone marrow will be collected at baseline, during the window period treatment with magrolimab + obinutuzumab, and at the time of disease progression.

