### **3.7.2 Follow-Up Visits – Prior to Disease Progression**

Patients who discontinue trial treatment for a reason other than disease progression will move into the Follow-Up Phase and should be assessed approximately as follows: every 3 months for two years after completion of study therapy, every 6 months for years 3-5, and then annually thereafter at the discretion of the investigator. Any other evaluations and tests should be performed as clinically indicated. After 5 years of monitoring without disease progression the decision to continue further surveillance imaging, including any assessments and procedures, will be left to the discretion of the investigator.

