### **5.3.6 Metabolic Tumor Imaging**

Under the direction of [name], special research analyses/readings of standard 18F-FDG PETs collected per standard of care will be performed to evaluate metabolic tumor volume and total lesion glycolysis.

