 Complete Blood Count with Differential will be performed prior to each dose and 3-6 hours after the first and second doses of magrolimab - Cycle 1, Days 2 and 8 for dose-finding arms (Arms 1 and 2), and Cycle -2, Days 2 and 8 for dose-escalation arms (Arms 3 and 4).

 Chemistry panels include: Acute care, Hepatic, and Mineral and 24-hour urine creatinine clearance (if needed to measure CrCl).

 Peripheral blood flow cytometry for diagnostic and staging purposes; repeat in follow-up to assess disease status and response. See also Section [5](#) for flow cytometry to be collected also for research purposes.

 Bone marrow aspiration ( $\pm$  flow cytometry)/biopsy within 12 months prior to starting treatment, unless repeat at screening/baseline felt to be clinically indicated (see Section [2.2](#)); repeat in follow-up to confirm response or progression only if bone marrow involvement is present at baseline.

 CT scans (preferred) of chest, abdomen and pelvis to be performed at each disease evaluation; may be adjusted to assess additional known sites of disease, as needed. Scans are to be done after completion of window with magrolimab and obinutuzumab (i.e., after 2 cycles of treatment; up to 7 days prior to Cycle 1, Day 1 pre-dose); after Cycle 3, Cycle 6, and Cycle 9 (if applicable), up to 7 days prior to next cycle; after Cycle 12 (if applicable), 21-28 days after completion of the treatment

 PET scans to be performed at baseline, after completion of the window with magrolimab and obinutuzumab, after Cycles 6 and 12 (if applicable), and at the end of treatment; repeat additionally if clinically indicated

 If adequate archival tissue at baseline, fresh tumor biopsy is optional. Optional “on-treatment” and bone marrow sampling will be performed, as indicated in Section [5](#).

 Samples for correlative research blood and saliva (preferred)/buccal swab samples to be collected as indicated in Section [5](#).

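### The radiation ceiling in 12.3.1.4 (7 CTs, 4 PET/CTs, 14.1 rem) is too low for the follow-up imaging that Appendix G schedules through year 5

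*Combined protocol and SAP*

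**What the plan says.** Section 12.3.1.4 lists the sources as "Up to 7 CT scan of chest abdomen pelvis (1 during screening", up to 4 FDG-PET/CT scans, and "Up to 2 CT-guided biopsies as referenced above". It then says "Subjects in this study may be exposed to approximately 14.1 rem" and converts this to a cancer risk of 1.4% and a fatal cancer risk of 0.7%. It names no period and excludes no class of scan.

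The CT-or-MRI row of Appendix G is marked at screening, baseline, the disease evaluations, end of treatment or progression, and the pre-progression follow-up visits. Footnote 11 reads "CT scans (preferred) of chest, abdomen and pelvis to be performed at each disease evaluation" and places scans after the window and after Cycles 3, 6, 9 and 12. Section 3.7.2 sets follow-up at "every 3 months for two years after completion of study therapy, every 6 months for years 3-5" and leaves surveillance imaging to the investigator only after five progression-free years. Footnote 4 of Appendix G gives the same intervals.

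Footnote 12 places PET at baseline, after the window, after Cycles 6 and 12, and at end of treatment. Footnote 3 repeats the end-of-treatment assessments at progression if treatment stopped for another reason.

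**The concern.** The ceiling is worded as a maximum for the whole study, but its CT count is nearly or fully used by the end of treatment for a patient who receives 12 cycles. Up to 14 scheduled follow-up scans then have nowhere to go.

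At stake is the only quantified radiation risk in the risk/benefit section. It would be too low for patients in long remission, which is the outcome the trial aims for in diseases with long survival.

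**Working it through.** **1. The plan's own figures.** 1.4% / 14.1 rem = 0.099% per rem. At a rounded 0.1% and 0.05% per rem, 14.1 rem gives 1.41% and 0.705%, which match the stated 1.4% and 0.7%. The conversion is sound. The 14.1 rem itself cannot be rebuilt, because no per-scan dose appears anywhere.

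**2. CTs through end of treatment (Appendix G, footnotes 1, 3 and 11).**
- Expansion, 12 cycles: screening, post-window, and Cycles 3, 6, 9 and 12 make 6. A separate end-of-treatment scan makes 7. A screening scan inside the baseline window is not repeated.
- Expansion, complete response (for CLL, also with undetectable MRD), stopping after Cycle 6: screening, post-window, and Cycles 3 and 6 make 4.
- Dose-finding, same response: there is no window, so 3.

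**3. Follow-up visits with CT or MRI.** 24/3 + 36/6 = 8 + 6 = 14.

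**4. CT totals against the stated 7, if every follow-up scan is a CT.**

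| Patient | Through treatment | Follow-up | Total | Passes 7 |
|---|---|---|---|---|
| Expansion, 12 cycles | 6 or 7 | 14 | 20 or 21 | month 6 or month 3 |
| Expansion, stops after Cycle 6 | 4 | 14 | 18 | month 12 (4 + 4 = 8) |
| Dose-finding, stops after Cycle 6 | 3 | 14 | 17 | month 15 (3 + 5 = 8) |

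**5. PET.** For a 12-cycle expansion patient, baseline, post-window, Cycle 6 and Cycle 12 use all 4. The repeat at a later progression is a fifth. A patient who stops after Cycle 6 has 3, and the progression PET makes 4, so that patient stays within the ceiling.

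**6. Dose (per-scan values are assumed).** Let c, p and b be rem per CT, PET/CT and CT-guided biopsy, with 7c + 4p + 2b = 14.1. It follows that c cannot exceed 14.1/7 = 2.01. For 12 cycles the total is 14.1 + 13c (20 CTs) or 14.1 + 14c (21 CTs).
- c = 0.5 with 13 extra CTs: 14.1 + 6.5 = 20.6 rem, or 2.1% (fatal 1.0%).
- c = 1.5 with 14 extra CTs: 14.1 + 21.0 = 35.1 rem, or 3.5% (fatal 1.8%).
- Equal dose for all 13 listed procedures: 14.1/13 = 1.085 rem each. The total is 14.1 + 13 × 1.085 = 28.2 rem, or 14.1 + 14 × 1.085 = 29.3 rem (2.8% to 2.9%).
- Expansion patient stopping after Cycle 6, equal dose: 18 CTs + 3 PETs + 2 biopsies = 23 procedures, and 23 × 1.085 = 25.0 rem (2.5%).

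A fifth PET adds p, which is 1.1 rem under equal doses. It combines with all 14 follow-up CTs only if progression comes after the last of those visits.

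**The case against.** **Surveillance scans are standard care.** Section 1.2.1 describes them that way, so they might have been left out on purpose. But 12.3.1.4 draws no such line, and Section 5.3.6 calls the PETs "standard 18F-FDG PETs collected per standard of care" although 12.3.1.4 counts them. This does not rescue the figure.

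**MRI is allowed and adds no radiation, and progression ends the schedule early.** Both are true, and both lower the exposure of many patients. They do not defend a stated maximum when CT is the preferred method.

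**Which 7 CTs are meant is not stated.** This stands. Footnote 11 puts the Cycle 12 CT 21 to 28 days after treatment, and footnote 3 lets the end-of-treatment assessment coincide with the 30-day safety visit, so the two may be one scan. A reader might infer that the list counts only on-treatment scans, but the seventh could be a follow-up or progression CT. At most one of the 14 would then fit, hence 13 to 14 extra CTs.

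**Three biopsies against two.** A reader might infer this from Section 3.1 ("Research biopsies of lymph nodes and/or bone marrow will be collected at baseline, during the window period treatment", and again at progression). The documents do not support it. The ceiling counts CT-guided biopsies only, CT guidance is optional, excision is preferred (Section 5.2.4.2), and a baseline biopsy is needed only if existing tissue is inadequate.

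**Re-treatment adds more.** It does, but it follows relapse, which ends pre-progression follow-up. Those scans do not simply stack on 14 follow-up CTs.

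**Conclusion.** The point holds as a count taken from the protocol's own schedule: up to 20 or 21 CTs for a 12-cycle expansion patient and 18 for an expansion patient who stops in complete response after Cycle 6, against a stated 7. A fifth PET is also possible for the 12-cycle patient, against a stated 4. It does not take a five-year remission to break the CT ceiling; a year or a little more of follow-up on CT is enough for responders who stop after Cycle 6.

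The size is less certain. For 12 cycles with full follow-up by CT, an assumed 0.5 to 1.5 rem per CT gives about 21 to 35 rem, and equal dose per procedure gives about 28 to 29 rem. A reader might infer that the stated risk is half the true one. That ratio rests on per-scan doses the documents do not give, and it shrinks with shorter follow-up or MRI. Nor is there a slip in converting rem to risk. The fault lies in what the total covers. The consent form was not available, so what participants are told about follow-up scans could not be checked.

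**What to change.** Recount CT and PET from Appendix G, including the follow-up and progression scans, and restate the rem, cancer and fatal-cancer figures in 12.3.1.4 and wherever they are repeated to participants. Alternatively, state that 14.1 rem covers only the treatment period and give the follow-up figure beside it. Either way, name the scans counted and the dose assumed for each type, and show re-treatment scans as a separate scenario.

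The cost is a dosimetry recalculation and a change of wording. The scan schedule stays as it is. The only downside is a less favourable stated risk.
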